5. TREATMENT OF SUBJECTS

5.1 Investigational medicinal products

Eligible subjects will be randomized to one of three treatment groups:

- Nanocort 75 mg IV infusion and IM saline injection, or
- Nanocort 150 mg IV infusion and IM saline injection, or
- Depo-Medrol 120 mg IM injection and IV saline infusion.

Subjects in this trial will be randomized to receive either Nanocort (75 mg/infusion or 150 mg/infusion) administered as an IV infusion, or 120 mg methylprednisolone acetate (Depo-Medrol®) administered as an IM injection. Subjects will receive treatment on Day 1 and Day 15 with additional study visits on Weeks 1, 2, 3, 4, 6, 8 and 12. Compliance will be recorded after dosing of Investigational Medicinal Product (IMP) at Day 1 and Day 15 (week 2).

IV infusion (either Nanocort/Placebo) will be administered over approximate 2.5 hours, with an increasing infusion rate over the whole infusion period. If required, infusion rate can be modified in case of infusion related reactions as per PI opinion. A detailed instruction will be documented the in the Investigational Medicinal Product (IMP) manual.

5.1.1 Nanocort arm

Prior to Nanocort administration, the contents of the requisite number of vials will be diluted up to 500 mL with normal saline (NaCl 0.9% w/v) and will be administered as IV infusion

In addition, these patients will receive IM normal saline (as placebo) in 3 ml in the same visit.

5.1.2 Depo-Medrol arm

On Day 1 and Day 15 subjects will receive IM injection of Depo-Medrol (3 ml) and 500 ml normal saline (as placebo) as IV infusion in the same visit.

The details of the preparation and administration of the IMP will be documented in the IMP manual.

5.1.3 Blinding

The study will be performed in a double blind, double dummy fashion. Each patient will receive an infusion and an IM injection containing either an active treatment or a dummy treatment. Opaque IV lines, sleeved bags and opaque syringes will be used to maintain blinding. The IMP preparation will be done by an independent unblinded person (pharmacist or designated person) in order to keep the Investigator and other site personnel blinded.

Proper care has to be taken so that the patient's treatment will not be disclosed to the patient, Investigator or other site personnel.

5.2 Use of co-intervention

Any medication the subject takes other than the study drug is considered a concomitant medication (co-medication). All co-medications must be recorded in the Electronic Case Report Form (eCRF). The following information must be recorded in the eCRF for each co-medication: generic name, route of administration, start date, stop date, dosage, and indication. Any changes in the dosage or regimen of a concomitant medication must be recorded in the eCRF. The subject should not take any concomitant treatment without the Investigator's knowledge. Investigator will instruct patients about co-medications and diet if required.

At Screening, subjects will be asked to provide details of all medications they have taken during the last 8 weeks. At each subsequent study visit (as listed in the Schedule of Assessments), subjects will be asked what co-medications they are currently taking.

During the study co-medications may be administered at the discretion of the Investigator in order to provide the subject with the best possible medical care. However, it is recommended that changes in ongoing treatments or introduction of new therapies are kept to a minimum. The risk/benefit to the subject should be carefully assessed and consideration given to the timing of any necessary introductions during the study period.

5.2.1 Allowed Medications

Co-medications that are allowed during this study include:

- Concomitant therapies taken for the long term treatment of pre-existing conditions (as per Investigator's opinion) may be continued during the study. However, these should be stabilized prior to entry and continued wherever practical without variation of dose or regimen during the study.
- Prescription medications for contraception and/or those medications deemed acceptable by the Investigator and Sponsor, or designee.
- Topical glucocorticoid GC creams are allowed, however subjects should not receive more than 100 gram of a mild to moderate topical corticosteroid cream per Week, 50 gram of a potent corticosteroid cream per week or 30 gram of a very potent topical corticosteroid cream per week in the 4 weeks prior to the Screening Visit and throughout the duration of the study.

- Inhaled glucocorticoids are allowed.
- Stable treatment with DMARD for at least 8 weeks prior to the Screening Visit and willing to continue current treatment for 12 weeks/throughout the study (this includes biologicals).
- Rituximab is only allowed when on a fixed dosing scheme of every 6 months.

5.2.2 Prohibited Medications

The following medication use is restricted and/or will exclude the subject from enrolment in this trial:

- Exposure to an experimental treatment or use of investigational product within the past 30 days prior to Screening, or is still within a washout period of a previous clinical trial.
- Last treatment with oral, rectal or injectable (including intra-articular) glucocorticoids (GCs) must be discontinued for at least 8 weeks prior to Screening Visit and may not be taken throughout the duration of the study.
- Previous treatment with IV gamma globulin, plasmapheresis or ProSORBA® column within 3 months prior to screening and during the study.
- Systemic antibiotics and/ or anti-viral medications for treatment of an active infection required at the time of screening.
- Immunizations or vaccinations during the study period.
- Medications that may cause drug-drug interactions with methylprednisolone in opinion of investigator

5.2.3 Escape medication

Investigator can use medicines in safeguard of patient if required.

5.2.4 Other RA medication

All subjects will be followed for 12 weeks. Subjects who do not reach at least a moderate EULAR response at week 2 or at any visit thereafter, may receive other RA medication. In this case, several QoL measurements may be skipped, see footnote in Table 2, Schedule of Assessments. The infusion at week 2 will take place and the patients remain in the study for the remaining visits for safety follow up.

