2.1 Intent-to-Treat Population

All patients randomized into the study will be included in the ITT population, if at least one dose or a part of Nanocort IV/Placebo infusion or Depo-Medrol/placebo IM injection was administered and at least one post-baseline efficacy measurement was performed.

Patients will be analyzed within the original treatment group they were randomized to. All analyses will be completed for the ITT population. The main analyses for assessment of study success will be analysis of the primary endpoint on the ITT population (see section 4.8).

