2.4 Safety Population

The safety population (SAF) will include all patients who receive at least one infusion or part of infusion with Nanocort/placebo or at least one IM injection or

part of IM injection with Depo-Medrol/placebo and had at least one post baseline safety assessment.

Patients will be assigned to treatment groups as treated for analysis.

3. Blinded Review of the Data

A blinded data review will be held before breaking the blind. The blinded data review will be performed by at least the Principal Investigator, the Medical Monitor, the Study Lead and the Trial Statistician. The goal of the blinded data review is to determine for each subject the maintenance of improvement at 12 Weeks, the protocol violations and to evaluate the impact of these protocol violations on the EULAR response.

The decisions taken during the blinded data review will be finalized and signed by participants on the blinded data review report before unblinding.

4. Statistical and Analytical Methods

This analysis plan gives a detailed description of the statistical methodologies, data listings, and summary tables planned in the analysis of the data in the CLR-15-05 study. This section describes the statistical analyses of the study based on the statistical section of the protocol (CLR15_05_Prot_V3.1_Amend_25Sep2017.pdf). Any difference with the protocol will be identified and documented. The statistical data analysis, described in this document, is intended to provide unbiased and valid conclusions concerning the objectives of the study.

This SAP describes only the analyses for the study objectives not involving the PK objectives. The PK objectives will be described in a separate analysis plan.

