4.2 Missing Data Handling

Imputation will be implemented for partial start/end dates of adverse events dates. If the start day is missing, impute the 1st of the month, unless month and year are the same as month and year of the first dose of study drug then impute the first dose date. If start day and start month are both missing, impute 1st January but if year is the same as year of the first dose date, then impute first dose date. If the end day is missing, impute the last day of the month. If end day and end month are both missing impute 31st December. No other imputation of missing data will be performed, and only available data will be presented.

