4.8.3 Other Secondary Analyses

All other secondary analyses will be completed for both the ITT and PP populations. EULAR response (good, moderate, no response) at Week 1, 2, 3, 4, 6, 8 and 12 will be summarized by treatment group and the treatment groups will be compared by using the non-parametric Wilcoxon-Mann-Whitney test.

DAS28 will be summarized and analyzed at Week 1, 2, 3, 4, 6, 8 and 12. The DAS28 score is calculated as follows:

$$DAS28 = (0.555 \times \sqrt{TJC}) + (0.284 \times \sqrt{SJC}) + (0.7 \times \log_e ESR) + (0.0142 \times GH)$$

where TJC = tender joint counts on 28 joints, SJC = swollen joint counts on 28 joints, GH = general health, i.e. patient's global assessment of disease activity (100 mm VAS) and ESR = erythrocyte sedimentation rate (mm/hr). If ESR was not available, then CRP may be used instead. See Appendix C for details on scoring and coding. At a particular timepoint, if one or more of the four components used in calculating DAS28 are missing, then the DAS28 will be considered missing at that timepoint.

If DAS28 scores are approximately normally distributed via visual inspection, then DAS28 scores at 1, 2, 3, 4, 6, 8 and 12 weeks will be analyzed using analysis of covariance (ANCOVA), including baseline scores and study site as covariates. If DAS28 scores are markedly non-normally distributed via visual inspection, then the Kruskal-Wallis test will be used to compare the groups at each time point. In addition to the group comparison, the time course of DAS28 scores will be submitted to a repeated measures analysis of variance, with treatment group, time and the interaction of treatment group and time in the model.

If the percentage change in DAS28 scores is approximately normally distributed via visual inspection, then % change at 1, 2, 3, 4, 6, 8 and 12 weeks will be analyzed using ANCOVA, including baseline scores and study site as covariates. If % change is markedly non-normally distributed via visual inspection, then the Kruskal-Wallis test will be used to compare the groups at each time point. In addition to the group comparison, the time course of % change will be submitted to a repeated measures analysis of variance, with treatment group, time and the interaction of treatment group and time in the model.

Time to first EULAR response (moderate or good) will be analyzed using the Kaplan-Meier method; comparison between the treatment groups will be performed using the log-rank test.

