Short Form 36 (SF-36) to assess physical and mental component at baseline, week 1, 2, 4, 6, and 12 will be summarized and analyzed. See Appendix A for details on scoring and coding. If the change from baseline is approximately normally distributed via visual inspection, then the change from baseline at 1, 2, 3, 4, 6, 8 and 12 weeks will be analyzed using ANCOVA, including baseline scores, age and gender as covariates. If the change from baseline is markedly non-normally distributed via visual inspection, then the Kruskal-Wallis test will be used to compare the groups at each time point.

Health Assessment Questionnaire (HAQ) at baseline, week 1, 2, 3, 4, 6, 8 and 12 will be summarized and analyzed. See Appendix E for details on scoring and coding. If the change from baseline is approximately normally distributed via visual inspection, then the change from baseline at 1, 2, 3, 4, 6, 8 and 12 weeks will be analyzed using ANCOVA, including baseline HAQ, baseline DAS28 and study site as covariates. If the change from baseline is markedly non-normally distributed via

visual inspection, then the Kruskal-Wallis test will be used to compare the groups at each time point.

FACIT Fatigue Scale at baseline, week 4 and 6 will be summarized and analyzed. See Appendix F for details on scoring and coding. If the change from baseline is approximately normally distributed via visual inspection, then the change from baseline at 1, 2, 3, 4, 6, 8 and 12 weeks will be analyzed using ANCOVA, including baseline FACIT, baseline DAS28 and study site as covariates. If the change from baseline is markedly non-normally distributed via visual inspection, then the Kruskal-Wallis test will be used to compare the groups at each time point.

Maintenance of Improvement at 12 Weeks assessed during a blinded review by the Medical Monitor (MM) and Principal Investigator (PI) at the end of the study will be compared between treatment groups using a stratified Cochrane-Mantel-Haenszel test, stratified by study site.

The Health Economics Questionnaire (HEQ) at week 12 will be summarized in a table of the responses for each treatment group as recorded on the questionnaire.

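### After week 2 the SAP does not say how efficacy data following permitted other RA medication are treated, and questionnaires skipped because of non-response are analysed on available data only

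*Combined protocol and SAP*

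**What the plan says.** Protocol 5.2.4 makes EULAR non-response the trigger for two things. The first is treatment: "Subjects who do not reach at least a moderate EULAR response at week 2 or at any visit thereafter, may receive other RA medication". The second is data collection: "In this case, several QoL measurements may be skipped". The footnote to the Schedule of Assessments that names these measurements is not in the text available to me. The section adds that "The infusion at week 2 will take place", and that these patients stay in the study for the remaining visits, with safety follow-up given as the purpose. Protocol 8.3 has DAS28 calculated at each study visit.

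Protocol 10.9 leaves the handling of missing clinical endpoint data to the SAP. SAP 4.2 imputes partial adverse-event dates and then says: "No other imputation of missing data will be performed, and only available data will be presented". For the ITT set, SAP 2.1 says: "Patients will be analyzed within the original treatment group they were randomized to".

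SAP 4.8.3 compares EULAR, DAS28, ACR, VAS and HAQ through week 12 without mentioning other RA medication. It also says "Time to first EULAR response (moderate or good) will be analyzed using the Kaplan-Meier method" and "Short Form 36 (SF-36) to assess physical and mental component at baseline, week 1, 2, 4, 6, and 12 will be summarized and analyzed". FACIT is collected at baseline and weeks 4 and 6. Under SAP section 3 the blinded review is to "determine for each subject the maintenance of improvement at 12 Weeks", with no stated handling of added medication.

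**The concern.** The outcome under study triggers both the added treatment and the permission to skip questionnaires. This has two consequences.

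- **Clinical endpoints.** A patient who fails at week 2, starts another RA drug and responds at week 6 is a week-6 EULAR responder, possibly an ACR responder, and a Kaplan-Meier event for the randomised arm. The week-12 comparison then describes the randomised drug plus whatever was added. That is a legitimate question, but the SAP does not say it is the one being asked.
- **Questionnaires.** Any that are skipped are missing because of non-response, and the planned ANCOVA uses the remaining patients. The available means lean towards those who did well. Patient-reported outcomes are a stated secondary objective (SAP 1.3.2).

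The size and direction of the effect depend on uptake by arm, for which no dedicated table is planned.

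**Working it through.** **No figure in the documents is at issue.** They give no uptake rate, no response rate after added medication and no skip rate. Everything below is assumed and shows only how far the analyses can diverge.

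**Inputs (assumed).** Week-2 response p = 0.70 in one arm and 0.50 in the other. The second infusion still takes place, so s = 0.20 of unmedicated non-responders respond later. Relapse among week-2 responders is l = 0.10. Uptake among those eligible is u, and response after added medication is r.

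**Week-12 response**

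- No added medication: p(1−l) + (1−p)s. This gives (0.63 + 0.06) − (0.45 + 0.10) = 0.69 − 0.55 = 0.14.
- Non-response rule: p(1−l) + (1−p)(1−u)s.
- As observed: the rule value + (1−p)ur + p·l·u·r.

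Differences in percentage points, with the same uptake in both arms:

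| u | Rule | As observed, r = 0.3 | r = 0.5 | r = 0.6 |
|---|---|---|---|---|
| 0.25 | 15.0 | 13.65 | 12.75 | 12.3 |
| 0.50 | 16.0 | 13.3 | 11.5 | 10.6 |
| 0.80 | 17.2 | 12.9 | 10.0 | 8.6 |
| 1.00 | 18.0 | 12.6 | 9.0 | 7.2 |

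Check of the last cell: (0.63 + 0.18 + 0.042) − (0.45 + 0.30 + 0.03) = 0.852 − 0.780 = 0.072.

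Unequal uptake at r = 0.5:

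- 50% in the better arm and 100% in the other: as observed 0.7525 − 0.7250 = 2.75 points; rule 0.66 − 0.45 = 21 points.
- 100% and 50%: as observed 0.8150 − 0.6375 = 17.75 points; rule 0.63 − 0.50 = 13 points.

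**First response by week 12**

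- No added medication: p + (1−p)s = 0.76 − 0.60 = 16 points.
- As observed: p + (1−p)[(1−u)s + ur]. This runs from 8.0 points (u = 1, r = 0.6: 0.88 − 0.80) to 15.5 (u = 0.25, r = 0.3: 0.7675 − 0.6125).
- Later first responses not counted: p + (1−p)(1−u)s, 17 to 20 points.

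**Questionnaires.** Let q be the share of non-responders whose questionnaire is skipped, and D the responder minus non-responder mean. The full-data difference is (0.70 − 0.50)D = 0.20D. The available-data difference is D × [0.7/(0.7 + 0.3(1−q)) − 0.5/(0.5 + 0.5(1−q))].

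| q | Missing by arm | Difference | Share kept |
|---|---|---|---|
| 0.125 | 3.75% v 6.25% | 0.194D | 97% |
| 0.25 | 7.5% v 12.5% | 0.185D | 93% |
| 0.50 | 15% v 25% | 0.157D | 78% |
| 0.80 | 24% v 40% | 0.088D | 44% |

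This last calculation leaves out late response, relapse and any effect of the added drug on the scores.

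**A second set of assumptions** for week 12 gives the same direction. Take 50% v 35% response without added medication, with all recipients otherwise non-responders. As observed is p + (1−p)ur. The 15.0-point difference becomes 13.9 points at u = 0.25, r = 0.3, and 4.5 at u = 1, r = 0.7.

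**The case against.** - **A supportive analysis exists.** A reader might infer that the plan has no alternative analysis at all. That is not so. SAP 2.2 and 4.8.3 repeat the secondary analyses in the PP set, whose exclusions include a catch-all for other relevant violations, with final criteria in a separate report I have not seen. But the listed criterion concerns prohibited DMARDs or biologicals, and 5.2.4 permits this medication. If PP did remove recipients, it would select on outcome.
- **Medication is tabulated.** SAP 4.9.5, Tables 24.A and 24.B and Listing 20 cover concomitant medication. They do not isolate RA drugs started after non-response, so what is missing is a subset table.
- **The later visits are described as safety follow-up.** It could be argued that efficacy data after added medication were never meant to count. Protocol 8.3 and SAP 4.2 point the other way, because DAS28 is calculated at each visit and available data are used. The ambiguity is a reason for the SAP to state the rule.
- **As-observed analysis is defensible.** This stands. The 14-point benchmark is a hypothetical that neither analysis targets, and at r = 0.3 the as-observed figure is closer to it than the rule.
- **The questionnaire part depends on an unseen footnote, and low skip rates do little harm.** Both are true. The remedy is conditional on the footnote.
- **Proportionality.** These endpoints lie outside the gatekeeping scheme in a trial that ended early with far fewer patients than planned. That favours a few simple additions.

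**Conclusion.** The concern holds for secondary endpoints after week 2. The SAP leaves unstated whether efficacy data after added medication count. Its available-data rule also gives outcome-selected comparisons for any skipped questionnaire.

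The size is unknown. Under the assumed rates, the as-observed week-12 difference is 7.2 to 13.7 points with equal uptake, against 14 without added medication, and 2.75 or 17.75 in the two unequal-uptake examples. At 25% uptake the effect is small. The questionnaire difference keeps 44% to 97% of its full-data value over the skip rates tried. No power statement is made, because enrolment is not given.

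Three stronger readings are not supported:

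- **The primary result is at risk.** The Day 8 endpoint comes before the provision starts, and the Day 15 key secondary endpoints are measured at the visit that first triggers it.
- **The as-observed analysis is wrong.** It answers a treatment-policy question. Naming it so changes no result by itself, which is why a second analysis is needed beside it.
- **DAS28 and VAS also need imputation.** Neither is described as skipped, and imputation would not address added medication unless later values were explicitly set to missing.

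**What to change.** In SAP 4.8.3, for the ITT set, fixed before unblinding:

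1. Flag the start of other RA medication from the start date and indication already recorded in the eCRF (Protocol 5.2), and add a subset table of uptake by arm.
2. Keep the as-observed analysis and state that it includes data after added medication. Add one supplementary analysis that counts EULAR and ACR as non-response after that date. In time to first response, a first response after that date is not an event; earlier responses remain events. Report Maintenance of Improvement with and without the same rule.
3. For SF-36 and HAQ, and for FACIT, as far as the footnote affects them, add to the available-data ANCOVA a simple mixed model or multiple imputation using earlier scores and EULAR response status. State whether the target includes the effect of added medication. For FACIT only baseline precedes week 4, so earlier scores will help little there.

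Protocol 5.2.2, Protocol 5.2.4 and SAP 1.2 should be reconciled on which RA medication is permitted after week 2; no clinical rule is proposed here.

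The cost is one derived flag, some SAP wording and a few extra secondary analyses in a small sample, so any imputation model must be simple. The non-response rule answers a different question and can overstate a drug-only difference (15 to 18 points against 14 with equal uptake), so it belongs beside the as-observed analysis as a supplement.

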6. INVESTIGATIONAL MEDICINAL PRODUCT

[figure not shown]
6.1 Name and description of investigational medicinal product(s)

Nanocort is provided as a sterile, white to off-white, translucent liposomal dispersion for IV infusion, in 20 mL glass, single use vials. Each vial contains nominally 5.0 mg/mL +/- 5% Prednisolone sodium phosphate, encapsulated inside the liposomes, dispersed in 10% w/v sucrose solution, buffered with phosphate buffer at a pH of 7.4 and a tonicity range of 280 to 400 mOsm/kg. The product needs to be stored refrigerated between 2 and 8 °C. Freezing needs to be avoided.

Name of Finished Product:

Pegylated Liposomal Prednisolone Sodium Phosphate (Nanocort)

Figure 1. Drug Product Diagram

Description of Investigational Medicinal Product:

Nanocort is a novel formulation containing prednisolone sodium phosphate [PhEur] as the drug substance encapsulated in PEGylated liposomes of approximately 100 nm (range 80 to 120 nm) that comprise a lipid bilayer of dipalmitoyl phosphatidyl choline (DPPC), cholesterol, and mPEG2000-distearoyl phosphatidyl ethanolamine (mPEG2000-DSPE) in a mass ratio of approximately 3.5:1:1. Coating of the liposome lipid bilayer with PEG improves the properties and performance of the formulation, including physical stability and prolonged circulation time in vivo. The lipid bilayer encloses an aqueous compartment in which the water-soluble sodium phosphate derivative of prednisolone is entrapped. The proposed formulation also includes the compendial excipients sucrose, sodium dihydrogen phosphate dihydrate, disodium hydrogen phosphate, absolute ethanol (removed during diafiltration process), and Water for Injection.

